A dramatic increase in the number of infants diagnosed with DP (Deformational Plagiocephaly) has been observed worldwide since the institution of the American Academy of Pediatrics' Back to Sleep Program.^{1, 16} It is estimated that the Neurosurgery and Plastic Surgery departments at Children's Hospital Boston (BCH) care for a minimum 2500 infants per year with positional DP. At present, because DP is considered a purely cosmetic condition, there are limited preventative and corrective resources available to parents and healthcare providers. Additionally, because it is believed to be a benign condition some infants with milder forms of DP may not be recommended for treatment. However, several recent studies have demonstrated associations between developmental problems and DP, leading some to question whether DP causes both skull and brain deformation.⁸⁻¹³ The purpose of this multidisciplinary descriptive pilot study will be to use brain MRI and a cerebral tissue oxygenation monitor called Frequency Domain Near Infrared and Diffuse Correlation Spectroscopy (FDNIRS/DCS) to describe if differences in brain structure and characteristics exist in infants with significant DP before and after correction of the deformational defect, and to seek preliminary evidence that might link DP with developmental delays.

Background and Significance

Incidence

The rate of Sudden Infant Death Syndrome has significantly declined since implementation of the American Academy of Pediatrics, Back to Sleep Program in 1992 by recommending that infants sleep in the supine position. However with this change in infant sleep position the incidence of DP has dramatically increased^{3, 16}. The incidence

of DP ranges between 3-48% (120,000-2 million) for all infants.⁶ Infants with DP have irregular or misshapen heads. DP develops as the infant's thin soft skull conforms to the flattened bedding upon which the infant is placed.⁷ Issues such as prematurity, lack of full bone mineralization, neurological deficits, preferential head position (torticollis), sedation, paralysis and limited tummy time increase the risk for DP.^{5, 8, 17, 18} While it is reported that some milder forms of DP resolve spontaneously, a recent study demonstrates that 39% of children without corrective action had persistent positional head shape deformity at age 3 to 4 years.⁷

Deformational Plagiocephaly in Full Term, Healthy Infants

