Some researchers and healthcare providers are concerned that DP may be more problematic than once thought. Concurrently, technological advances now allow researchers to detect diminutive changes in brain structure. In this multidisciplinary descriptive pilot study we will use brain MRI and a cerebral tissue oxygenation monitor to describe if a difference in brain structure and characteristics exist in infants with significant DP before and after correction of the abnormality. Knowledge generated from this study will enable investigators to seek preliminary evidence that brain development is influenced by the shape of the cranial vault, and that changes in brain structure and characteristics occur with helmet therapy. Additionally this study will help to determine the need for a larger investigation of this phenomenon that would further establish an association between DP and developmental delay.

Specific Aims

1. Specific Aim: To describe if differences in brain volume/structure exist by Brain MRI in a sample of infants prior to and following treatment of significant DP with helmet therapy.
2. Specific Aim: To describe if differences in myelination of axonal pathways exist by Brain MRI in a sample of infants prior to and following treatment of significant DP with helmet therapy.
3. Specific Aim: To describe if differences in myelination of axonal pathways exist by Brain MRI in a sample of infants with significant DP compared to infants with similar characteristics but less severe or no DP.
4. Specific Aim: To describe if differences in perfusion of cerebral structures exist by brain MRI in a sample of infants prior to and following treatment of significant DP with helmet therapy.
5. Specific Aim: To describe if differences in cerebral oxygen consumption by Frequency Domain Near Infrared and Diffuse Correlation Spectroscopy (FDNIRS/DCS) exist in a sample of infants prior to and following correction of significant positional head shape deformity
6. Specific Aim: To describe the cognitive ability in five areas of neurobehavioral development in a sample of infants with DP prior to and following helmet treatment using the Mullen Early Scales of Learning (MSEL).

Research Design and Methods

Design: This is a descriptive pilot study.

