Setting: Infant participants meeting inclusion and exclusion criteria will be enrolled through the outpatient plagiocephaly clinics (Neurosurgery and Plastic Surgery clinics) at Boston Children's Hospital, Boston Children's Hospital Waltham and Boston Children's Physicians South (Weymouth)

Table 1.

Inclusion Criteria	Exclusion Criteria

- DP requiring helmet therapy-Term gestation at birth (37 weeks or greater)-Less than/or equal to 8 months of age-No history of major health problem such as birth injury, genetic disorder, intracranial hemorrhage, hydrocephalus, neurologic abnormality-No history of implantable metal device or internal/external orthotic device	
- DP not requiring helmet therapy-Premature gestation at birth (less than 37 weeks gestation).-Greater than 8 months of age-History of major health problem such as birth injury genetic disorder, intracranial hemorrhage, hydrocephalus, neurologic abnormality-History of implantable metal device or internal/external orthotic device-Infants not completing prescribed treatment for correction with a helmet

Primary Study Sample: We believe that a sample size of 10 subjects meeting the inclusion and exclusion criteria in Table 1., will provide enough information to determine the need for a larger investigation of this phenomenon. To ensure the desired sample size of 10 subjects, a convenience sample of 10-15 infants (that includes 5 additional patients for attrition) with DP, recommended for treatment with helmet therapy, will be recruited into this study.

Comparison Sample: In Aim 2 we will retrospectively identify a sample of infants with similar characteristics (gender, age and race/ethnicity), with a less severe form of DP, or no DP to serve as comparisons.

Staff Education: All research staff will be Citiprogram trained. Also, research staff involved in recruiting, consenting and data collection procedures will receive training by the study PI.

Human Subjects: Prior to initiation of study procedures IRB approval will be obtained. The risk of a serious adverse event is unlikely in this study; however there are other inconveniences and risk to participation to be considered as follows:

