Families who attend/complete both sets of MRI measures (pre and post), will be offered a \$50 gift card at the end of the study to offset some of the gas costs incurred driving to the MRI appointments. In instances where families attempt the MRI but the baby cannot be effectively scanned due to movement, the families will still receive their gift card. Families who do not wish to attend the MRI, cancel their MRI appointments without rescheduling, or fail to arrive at their MRI appointments will not be eligible for the gift cards. The gift card may be given to the family at the end of their last MRI appointment if available, or will be mailed to them after they complete the study. If mailed to the family, they will receive a written thank you letter along with the gift card.

Comparison sample: To identify infants with similar characteristics but less severe or no DP, our neuroradiology team members will conduct a retrospective chart review from within BCH medical records. Infants with similar characteristics but with no or less severe DP as measured according to *Cranial Index and Cranial Symmetry Measures* (see *Head Shape Measures section below*) will be identified as our comparison sample. This will enable us to provide descriptive comparisons of Brain MRI axonal pathway myelination between infants with less severe or no DP.

Study Timeline

This pilot study will take approximately 1.5 years to complete.

Table 2.

Month 1	Month 2-4	Month 2-10	Month 8-10	Month 11+
IRB Application, Approval, Education of	Enrollment, Head Shape Measures	Treatment for DP	Head Shape Measures Brain MRI	Data Analysis &

clinical and study staff	Brain MRI FDNIRS/DCS MSEL		FDNIRS/DCS MSEL	Manuscript Preparation
--------------------------	---------------------------------	--	--------------------	------------------------

- Average time for treatment of DP is 4-6 months.

Head Shape Measures

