Cranial Index and Cranial Symmetry Measures: To ascertain that correction of the infant's head is achieved routine cranial index and cranial symmetry measures obtained at the NOPCO brace center, will be reviewed by the study team. The cranial index, is an objective measure that quantifies head shape by dividing the head width (M-L) by length (A-P) then multiplying it by 100% ¹⁸. The normal cranial index measurement is between 73%-85% is used to assess for brachycephaly or scaphocephaly. To assess for DP, the right anterior-posterior measures and left anterior-posterior measures will be used. For this measure, an 8mm difference in the right and left anterior-posterior measures will be indicative of asymmetry. In addition, and also as part of their routine care, a licensed orthotist will use a surface laser scanner to secure a computer image of the infant's head. The FastSCAN Handheld Laser Scanner to quickly and conveniently digitize the three-dimensional surface of the infants' head. Scanning involves smoothly sweeping the FastSCAN Wand over the infant in a manner similar to spray painting. An image of the object appears simultaneously on the computer screen. This type of measure, though fairly new, provides great detail, is reported to be nearly 100% accurate when used to make custom helmets and allows for a second set of measurements to be recorded. Measurements including A-P (length), M-L (width), Right anterior-posterior, Left anterior-posterior, and head circumference will be obtained and recorded.

Outcome Measures

Brain Magnetic Resonance Imaging (MRI): Is a routine diagnostic exam that uses a large magnet, radio waves and a computer to produce 2- and 3-dimensional images of the child's brain. This exam is FDA and does not use ionizing radiation (as in x-rays) and thus, is a way to better evaluate various parts of the body. Furthermore this type of exam is painless, since the scanner takes pictures without touching the child's body.

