with the MDI (.30). Similarly, the Mullen Receptive Language scale had a higher correlation with the Preschool Language Assessment Auditory Comprehension (.85) than with Verbal Ability (.72), while the converse was true with the Mullen Expressive Language Scale (.72 for auditory and .80 for verbal). Finally, the Mullen Fine Motor scale was strongly correlated with the Peabody Fine Motor Scale, across four age groups of children between the ages of 6 and 36 months (correlations ranged from .65 to .82). (2) Predictive validity: no information available.⁶⁴

Brain MRI axonal pathway

The identification of the comparison sample will enable us to provide descriptive comparisons of brain MRI axonal pathway myelination between with infants in our primary study sample against those with less severe or no DP.

Using the Cranial Index and Cranial Symmetry Measures, a comparison sample of infants (gender, age and race/ethnicity) with less severe or no DP will be identified by our neuroradiology team members through retrospective chart review from within BCH medical records. Data collection will be limited to Brain MRI and infant characteristics' data that already exists in the medical records. Data including brain MRIs and infant characteristics will be de-identified for storage. Members of the study team will maintain an electronic record of corresponding MRNs in the study log in the event that data verification or additional analyses are needed.

Axonal pathways for infants with DP primary study sample undergoing helmet therapy and those of the comparison sample will be constructed then examined for differences axonal pathways.

Data Management

Data will be managed and stored by the Cardiology Clinical & Research Regulatory Group at BCH. Baseline cranial index and cranial symmetry measurements (obtained manually and by laser scan) for each of the study subjects will be examined by one the investigators (Neurosurgeon or Plastic Surgeon) to confirm correction. Then one of the other investigators (a neuroradiologist with experience in performing FDNIRS/DCS and Brain MRIs) will examine each of the study subjects independently for changes in brain volume/structure, myelination of axonal pathways, perfusion of cerebral structures and cerebral oxygen consumption for changes pre and post correction. FDNIRS/DCS, brain MRI and MSEL data will be stored into a password protected, secure computer.

Data Analysis

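### Aim 3 comparators are classed on head shape alone, regardless of treatment history or timing, so an infant whose significant DP was already corrected could enter the comparison sample

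*Combined protocol and SAP*

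**What the plan says.** Specific Aims, Aim 3, compares myelination of axonal pathways "in a sample of infants with significant DP compared to infants with similar characteristics but less severe or no DP". It is the only aim that sets one group of infants against another.

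The comparators are found by retrospective chart review. The Comparison sample paragraph of Study Procedures describes them as "Infants with similar characteristics but with no or less severe DP as measured according to" the cranial index and cranial symmetry measures, and points to the Head Shape Measures section. The section on brain MRI axonal pathways repeats the rule: "Using the Cranial Index and Cranial Symmetry Measures, a comparison sample of infants (gender, age and race/ethnicity) with less severe or no DP". The sample paragraph below Table 1 lists what must be similar: "infants with similar characteristics (gender, age and race/ethnicity), with a less severe form of DP, or no DP". (That paragraph assigns the comparison to Aim 2, whereas Specific Aims makes it Aim 3.)

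The Head Shape Measures section gives the purpose of these measures: "To ascertain that correction of the infant's head is achieved routine cranial index and cranial symmetry measures obtained at the NOPCO brace center" are reviewed by the study team. It adds a threshold: "an 8mm difference in the right and left anterior-posterior measures will be indicative of asymmetry".

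**The concern.** One yardstick does two jobs. It certifies that a treated head has been corrected, and it decides who counts as an infant with milder or no DP. A corrected infant meets the second test because the first has been met, and an infant in mid-treatment may read as a milder case. The rule does not ask whether the shape was always like that or was brought there by a helmet.

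The study asks whether skull shape influences brain development. If it does, and if some of that influence outlasts correction, such comparators carry part of the effect they are meant to lack. The Aim 3 contrast would then be smaller than it should be. The pilot is meant to inform whether a larger study is needed, so a small or absent difference could be misread as evidence that skull shape does not matter.

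**Working it through.** **1. Does any other rule close the gap?**
- Matching covers gender, age, and race or ethnicity. Earlier DP severity and helmet history are not listed.
- Table 1 excludes infants with a history of an orthotic device, but it is attached to the primary sample. It cannot govern comparators as written, because it also requires DP that needs a helmet.
- No section says when the classing measure is taken relative to the MRI.

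The gap is therefore open on the text.

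**2. Which infants could pass through it, by age?**
Inputs: usual start of treatment at 3 to 6 months (Study Procedures); average treatment of 4 to 6 months (note to Table 2); enrollment up to 8 months of age (Table 1).
- Earliest completion: 3 + 4 = 7 months. Latest: 6 + 6 = 12 months.
- Completed by 6 months: none.
- Completed by 8 months, assuming start and duration are independent and uniform: the start-by-duration rectangle has area 3 × 2 = 6. The region where start plus duration is at most 8 is a triangle of area 0.5. The share is 0.5 / 6 = 8.3% of treated infants.

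If comparators are age-matched to pre-helmet scans, fully corrected infants overlap only at about 7 to 8 months. Part-treated infants could enter earlier, but the documents do not say how fast correction proceeds. If comparators are matched to post-helmet scans, at about 7 to 12 months, the ages overlap fully. The section on axonal pathways does not say which scan of the primary sample is used.

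**3. How much contrast is lost?**
Let Δ be the true difference in a tract measure between significant DP and correctly classed comparators. Let f be the fraction of comparators with earlier significant DP, and r the share of Δ that persists in them. With pre-helmet primary scans:
- Primary mean = μ + Δ
- Comparator mean = μ + f × r × Δ
- Difference = Δ × (1 − f × r)

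The documents give neither f nor r, so the range is shown:

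| r | f = 10% | f = 20% | f = 30% | f = 50% |
|---|---|---|---|---|
| 0 | 100% | 100% | 100% | 100% |
| 0.5 | 95% | 90% | 85% | 75% |
| 1 | 90% | 80% | 70% | 50% |

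The number of comparators is not stated. If it were 10, like the primary sample, two such infants would make f = 20%.

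**4. What if the helmet itself alters the tracts?**
Let h be such a shift in the helmeted comparators, here taken as the same fraction f. Against pre-helmet primary scans the difference becomes Δ × (1 − f × r) − f × h. The sign of h is unknown, so this part of the bias can go either way.

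**The case against.** The strongest reply is that few such infants will be found.
- **Existing MRI.** The section on axonal pathways limits collection to data already on file, so a comparator must already have had a brain MRI. The Inconvenience paragraph describes the study visits at Waltham as testing outside routine helmet care, and Study Procedures shows that this testing includes the MRI. Helmet patients therefore do not routinely have the scan.
- **Source of the measures.** The MRI section also derives the cranial index from the scan itself, so a brace-center record is not the only route to that measure.
- **Age matching.** It leaves little room for fully corrected infants if Aim 3 uses the pre-helmet scan, which best fits its wording about significant DP.
- **Purpose.** Aim 3 is descriptive, has no planned between-group test, and admits milder DP on purpose.

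Most of this stands, and it limits how often the problem can arise. It does not close the gap. A cranial index read from the scan still shows the corrected shape. Age matching does not remove part-treated infants, and it protects only if the pre-helmet scan is the one used, which is not stated. A descriptive analysis does not help either, because the bias lies in the group means whether or not a test is run.

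A reader might infer that contamination is likely, since the hospital departments "care for a minimum 2500 infants per year with positional DP". That is the wrong pool: the relevant infants are those with an MRI already on file, and the documents do not say how many of them wore a helmet.

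**Conclusion.** The point holds as a possible and unguarded misclassification in the only between-group contrast. As written, the rule would class a corrected or part-corrected infant as having milder or no DP. Its frequency is unknown and may be low.

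The size is conditional. At f = 20%, the contrast kept runs from 100% (r = 0) through 90% (r = 0.5) to 80% (r = 1). These figures assume pre-helmet primary scans and no separate helmet effect. If Aim 3 used post-helmet scans, the primary infants would themselves be corrected and this formula would not describe the contrast.

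Two stronger readings are not supported. One is that the Aim 3 difference is necessarily biased toward zero. That needs an effect that persists after correction, which the documents do not establish, and a helmet effect could push either way. The other is that more infants would be needed to keep power. No test is planned for this contrast; the signed-rank test in Data Analysis is for paired observations. The change is worth making because it is cheap, not because a large bias has been shown.

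**What to change.** In the Comparison sample paragraph of Study Procedures and in the section on brain MRI axonal pathways, state that:
1. an infant with any cranial orthosis treatment before or at the time of the MRI is not eligible as a comparator, or is shown separately;
2. severity is classed by the most severe head-shape value on record up to the date of the MRI, where earlier values exist;
3. Aim 3 uses the primary sample's pre-helmet scan.

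The cost is one extra item in a chart review already planned and a slightly smaller comparator pool. If the pool proves too small, showing affected infants separately keeps them in view without mixing them in. The second rule cannot help where no earlier head-shape value was recorded, and these changes do not supply a cut-off for milder DP, which the plan also leaves undefined. No infant's care is affected.

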Brachycephaly is one form of DP. Brachycephaly is reported to result from the infant's head resting on a firm mattress or other solid surface when in the supine position. Common in term infants, this deformation is characterized by occipital flattening (unilateral or bilateral), ear misalignment, frontal bossing, and facial asymmetry.¹⁹ This form of DP has become more prevalent since initiation of the Back to Sleep campaign by the American Academy of Pediatrics (AAP) and other guiding agencies during the 1990's.^{5, 6, 19, 20} The Back to Sleep campaign recommends parents place their infants supine to sleep and this change in sleep position has resulted in a dramatic decline in Sudden Infant Death Syndrome.¹

Plagiocephaly is another common form of DP associated with the supine sleeping position and the Back to Sleep campaign.^{20, 21} Plagiocephaly usually results from the head being positioned in the same direction repeatedly and may or may not be related to congenital muscular torticollis.^{5, 22} With this type of head shape deformity there is asymmetry of the head shape (one side of the occiput is flattened), and ear misalignment can be present.

Dolichocephaly is a narrow, elongated head shape. This deformation develops when the infant is frequently placed in the prone or sidelying-position and is commonly seen in the premature infant population and rarely observed in full term infants.^{18, 23} The actual incidence of dolichocephaly is not known, though infants that are sick or recuperating from illness, and spend more time in their beds in the prone position, are more vulnerable to developing this type of positional head shape deformity.²³

Social Impact of Deformational Plagiocephaly

The literature is replete with documents to support the claim that the undesirable head shape and facial features associated with DP can lead to problems with parent infant attachment and social isolation as the child grows.⁸⁻¹¹ This is because parents of infants with positional head shape deformities find their infant to be less attractive. In fact, parents are so concerned about DP that a recent search of the Internet revealed a number support groups for parents, allowing them to share their concerns and obtain information about this common problem.²⁴⁻²⁷

Neurodevelopmental Impact of Deformational Plagiocephaly

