The cranial vault is made up of several plates of bone that are separated by sutures. The bone plates allow protection for the brain while the sutures allow for expansion and growth of the brain. Brain growth is rapid during the first three years of life. During normal growth it is believed that cells in the dura mater, a lining of the brain respond to brain expansion and influence bone growth.²⁸ However, it is not known to what extent brain development is impacted when this normal process of brain expansion and bone growth is disrupted.

Much of the work with respect to cranial structure, brain development and developmental delay has involved infants with craniosynostosis.²⁹ Craniosynostosis is a severe condition that results in inadequate brain growth from premature fusion of one or more sutures of the skull, and requires surgical intervention to prevent long-term untoward neurodevelopment outcomes.²³

More recently though, some investigators are hypothesizing that DP may cause developmental problems in infants from the abnormal formation of the brain due to impaired expansion and compression from the deformed skull. This hypothesis, developed in response to numerous anecdotal and published reports linking DP (an unintended consequence of the Back to Sleep Program to prevent Sudden Infant Death Syndrome) to gross/fine motor delays, problem solving difficulties, communication deficits, vision/hearing problems and delayed developmental milestones, and has resulted in a broader examination of this phenomenon^{7, 20, 21, 30-33}, beyond the aesthetics.

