In review of the literature, one study of 287 infants with DP, 36% of parents reported that their child had one or more developmental delays such as gross motor delays, problem solving difficulties, and personal-social problems.⁷ Similarly, another study comparing toddlers with and without DP showed that toddlers with DP scored lower than demographically similar, but unaffected peers using the Bayley Scales of Infant Development III.³⁴ Additionally, in 2002, Balan et al demonstrated depressed cortical sound processing, indicative of dysfunction in auditory processing, in a sample of infants with posterior DP when compared to infants without DP.¹² Furthermore, Siatkowski et al in 2005, studying the visual fields of 40 infants with DP found that 35% had constriction of one or both hemifields by at least 20 degrees, suggesting that DP may affect visual field development. However Siatkowski also reported that there was no correlation between laterality of the constriction, to laterality of the asymmetry.³⁵

With these mounting concerns over the associations between DP and untoward outcomes, healthcare providers now question the long held belief that DP is a purely cosmetic condition. Some now hypothesize that there may be a spectrum of untoward outcomes that result from brain remodeling and this may depend upon the extent to which the skull is misshapen.^{14, 15} Thus investigators are now reevaluating whether or not DP is linked to neurodevelopmental problems.¹³

Technological Advances

Magnetic Resonance Imaging (MRI). MRI offers a safe alternative to other radiologic imaging techniques. This is because MRI uses a strong magnet instead of radiation to make images of the body's interior. The clarity and detail of the pictures from the MRI studies allow for the examination of the human body structures and functions. Therefore in recent years, MRI has become the tool of choice for examining the newborn and infant brain and in this study an MRI of the brain will permit the examination of brain volume, myelination and perfusion. Furthermore newly discovered methods for obtaining sedation free MRI's will be employed by the investigators.

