Inconvenience: If recruited at Boston Children's Hospital Waltham or Boston Children's Physicians South (Weymouth), study subjects and their parents may be asked to go to Boston Children's Hospital on two separate occasions to complete the cerebral tissue oxygenation monitoring. Parents will be given the option to decline this testing.

All study subjects and parents will be asked to return to BCH Waltham on two separate occasions to have testing that is not part of the routine management for DP with helmet therapy. Parents will not be compensated for their time, the cost of transportation or parking during these visits, and the visits will last approximately 2 ½ hours. In the event that the study team is unable to obtain measures during the scheduled visits due to time limitations, parents will be given the option to schedule additional appointments to complete the measures. There will be no obligation to attend these appointments.

Risk with Brain MRI: MRI is considered a safe FDA approved procedure with no inherent risk to the study subjects; however significant injury can occur to individuals with implantable or external metal devices that undergo MRIs. Therefore, all MRIs will be performed by, appropriately credentialed, BCH personnel. All study subjects will be thoroughly screened to be sure they have no implantable or external metal devices upon enrollment, during consent and prior to each MRI study. Additionally, parents of all study subjects will be asked to change their infant into (hospital or own) attire that is free of metal prior to each MRI study. Furthermore since the Brain MRI requires that the infant remain still for approximately ½ hour, anecdotal evidence suggests there is a 50% chance that a Brain MRI will not be able to be obtained on the first attempt necessitating the need for a repeat visit.

Risk with FDNIRS/DCS: The use of American National Standards Institute (ANSI) and Food and Drug Administration (FDA) approved light levels does not involve any known risk. The laser light used to make the measurements has very low power and is considered to present minimal risk—that is, no more risk than the subject would encounter in everyday life. The light intensity used with this device is many times less

then the amount of near infrared light the subject would receive during an outdoor walk on a sunny day.

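### In treated infants no planned analysis relates head shape to brain change, so the group pre/post summaries cannot separate growth common to all infants from an influence of cranial shape

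*Combined protocol and SAP*

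**What the plan says.** The Purpose Statement says the study will let investigators "seek preliminary evidence that brain development is influenced by the shape of the cranial vault" and will help decide whether a larger investigation is needed.

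Head shape in treated infants has two stated uses.
- **Confirming correction.** Under Head Shape Measures, "To ascertain that correction of the infant's head is achieved routine cranial index and cranial symmetry measures obtained at the NOPCO brace center" are reviewed by the team. Data Management repeats that a surgeon investigator examines these measurements to confirm correction.
- **Comparing image types.** Under Outcome Measures, cranial index is also measured on 3D MRI reconstructions of scalp and brain, to see which image type better quantifies interval change.

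Right and left anterior-posterior (A-P) lengths are recorded, and a difference of 8 mm indicates asymmetry. Study Procedures has head shape measured before treatment and again at completion and resolution. Outcome Measures plans hemispheric volumes, lobar parcellation, bilateral tract FA and MD, and regional perfusion.

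Data Analysis plans case presentations, mean, median, mode and frequencies and, if the data permit, a signed-rank test of paired differences against zero. Aim 3 adds a comparison of myelination "in a sample of infants with significant DP compared to infants with similar characteristics but less severe or no DP", using MRIs already in the medical records.

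**The concern.** The post-treatment measures come after an average of 4-6 months of treatment (Study Timeline), in infants enrolled at 8 months or younger. The protocol's background says "Brain growth is rapid during the first three years of life". Volume, myelination, perfusion, oxygen consumption and developmental performance may all shift over that interval whatever the skull does. A group pre/post difference is therefore expected from growth alone.

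The background also raises the idea that outcomes may depend on how misshapen the skull is, yet nothing in the aims or Data Analysis uses degree, change or side of deformity as an explanatory variable in treated infants. At stake is the pilot's main use. A change that ordinary growth would also produce says little about whether cranial shape deserves a larger study.

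**Working it through.** **1. Plan's own figure.** The target of 10 infants is a judgement, with no effect size, SD, alpha or power, so no formula can reproduce it. Only the attrition arithmetic can be checked: 10 + 5 = 15, and 10/(1 − 1/3) = 15.

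**2. Why the summaries cannot separate the two.** Write each infant's paired change as growth + shape effect + noise. The mean, median and signed-rank statistic depend on the sum of the first two terms. Growth of 1 SD with no shape effect, and no growth with a shape effect of 1 SD in every infant, give the same distribution of differences.

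**3. Likely number of paired scans.** Inputs: 10-15 recruited (Primary Study Sample); about 75% scan success (Outcome Measures); and, under Risk with Brain MRI, "there is a 50% chance that a Brain MRI will not be able to be obtained on the first attempt". A 50% rate with one repeat is 1 − 0.5² = 75%. Assume the two time points are independent and ignore other losses.
- 75% at each: 0.75² = 0.5625; × 10 = 5.6, × 15 = 8.4.
- 75% with one repeat: (1 − 0.25²)² = 0.879; × 10 = 8.8, × 15 = 13.2.

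That gives roughly 6-13 pairs. With 5 pairs, the smallest exact two-sided signed-rank p-value is 2/2⁵ = 0.0625.

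**4. Growth only, no shape effect.** Simulation of 400,000 studies, exact two-sided signed-rank test at 5%. The plan gives neither level nor sidedness, and growth is assumed in SDs of the paired change. Share of studies significant:

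| n | 0.5 SD | 1 SD | 2 SD |
|---|---|---|---|
| 10 | 28% | 78% | 100% |
| 8 | 19% | 61% | 99% |
| 6 | 11% | 35% | 87% |

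**5. Flattened-minus-opposite contrast.** Growth shared equally by both hemispheres cancels. With symmetric growth and no shape effect, the same test rejects in 5%, 4% and 3% of studies at n=10, 8 and 6.

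Normal left-right asymmetry in growth does not cancel if most infants are flattened on one side. Assume asymmetry of 0.5 SD, 80% flattened on the same side and between-side correlation of 0.5 to 0.8. The contrast then rejects in 12-21% (n=10), 9-15% (n=8) and 6-9% (n=6). With 60% on the same side it is 6-7% at n=10.

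**6. Telling asymmetry from a shape effect.** Let a be normal left-minus-right asymmetry in growth and s the shape effect (flattened minus opposite).

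| Coding | Left-flattened | Right-flattened |
|---|---|---|
| Flattened minus opposite | s + a | s − a |
| Left minus right | a + s | a − s |

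On flattened-minus-opposite coding, s keeps its sign across the two groups and a flips. On left-minus-right coding, a keeps its sign and s flips. The listing needs both groups. If 80% are same-side, the chance that all infants fall in one group is 0.8ⁿ + 0.2ⁿ = 11% (n=10), 17% (n=8) or 26% (n=6).

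**7. Precision of a correlation.** For an assumed Spearman correlation of 0.6, the 95% interval (Bonett-Wright) is tanh(atanh 0.6 ± 1.96 × √((1 + 0.6²/2)/(n − 3))). This gives −0.11 to 0.90 at n=10, −0.25 to 0.93 at n=8 and −0.49 to 0.96 at n=6.

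**The case against.** The strongest reply is that this is a descriptive pilot. Every aim is to describe, the test is conditional on the data, and it answers the question it is set: whether paired change differs from zero. All of that stands.

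Parts of the plan also go further than pre/post change.
- Aim 3 selects comparators by head shape and matches on age, which gives some control for growth. It covers myelination only, uses existing scans and plans no measure of change.
- The MRI cranial index is a width-to-length ratio, so uniform growth leaves it unchanged.
- Case presentations and the neuroradiologist's infant-by-infant review may show a pattern in single infants, although Data Analysis ties those comparisons to the aims and no aim links head-shape change to brain change.

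Three stronger readings are tempting but unsupported. A reader might infer that head shape serves solely to confirm correction; the MRI cranial index and the choice of comparators show otherwise. A reader might take 28%, 78% and 100% as false-positive rates; they are the chance of detecting a real pre/post change that happens to be growth. A reader might infer that an aim fails; none does.

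It can also be said that the side contrast is weak. The intervals are very wide. The protocol describes bilateral as well as unilateral flattening. It also cites a visual-field study in which "there was no correlation between laterality of the constriction, to laterality of the asymmetry". These limits stand, and they are why the addition should be descriptive.

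**Conclusion.** The concern holds as a gap between the stated purpose and the planned analysis, and calls for a cheap improvement rather than a correction of an error. In treated infants, the group pre/post summaries and signed-rank test cannot separate common growth from an influence of cranial shape. The exceptions are the age-matched myelination contrast, the MRI cranial index and single-infant descriptions.

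That conclusion follows from the structure of the paired difference and needs no assumed figure. The size does: the growth-only rates rest on assumed growth, a two-sided 5% level and normal noise, and the contrast's rates also on assumed asymmetry, side mix and between-side correlation. The documents give none of these.

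**What to change.** Add one exploratory paragraph to Data Analysis and keep every planned summary.

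1. Before images are read, fix in writing the rule that derives the flattened side from baseline right and left A-P lengths, using the protocol's own 8 mm criterion. Describe infants below it separately, against change in cranial index.
2. Report pre/post change in hemispheric and lobar volume, tract FA and MD, and regional perfusion for the flattened side, the opposite side and flattened minus opposite. Show the last separately for left-flattened and right-flattened infants. On that coding a shape effect has the same sign in both groups and normal growth asymmetry has opposite signs.
3. Plot each infant's change in flattened-minus-opposite brain measure against change in flattened-minus-opposite A-P length. Code both axes by baseline flattened side, show the scan interval, and give Spearman's correlation with a 95% interval. Make no significance claims.
4. State in the report that whole-brain, FDNIRS/DCS and MSEL changes remain confounded with growth and are not addressed by this contrast.

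The cost is that paragraph and the written rule, with no new data. The report should state these limits:
- intervals are very wide at about 6-13 paired scans;
- asymmetric growth with mostly same-side flattening can mimic an effect, and the split listing cannot reveal it if all infants are flattened on one side;
- bilateral flattening and effects equal on both sides are missed;
- the range of head-shape change may be narrow, because infants are re-measured at resolution;
- a volume contrast may show brain displaced by skull shape rather than altered development, a mechanism the background itself raises for dolichocephaly in preterm infants;
- a null contrast does not rule out a shape effect.
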